5.6.2 Deviations from prescribed follow-up windows

In order to ensure representative data for each data collection time-point, any time-point-specific trial data (quality of life and symptom scores) generated outside of the following windows will be regarded as missing and will not be used towards analysis:

- "One month visit" Day 21 post randomisation to day 56 post randomisation
- "Three month visit" Day 70 to day 112
- "Six month visit" Day 140 to day 196

5.7 Sensitivity analyses

5.7.1 Missing data

Sensitivity to missing data for the primary outcome will be assessed under a range of missing-not-atrandom scenarios. This will be performed using the following formula:

$$\Delta = \Delta_{\rm CC} + Y_1 P_1 - Y_2 P_2$$

where Δ is the treatment effect under the missing-not-at-random scenario, Δ_{CC} is the treatment effect under a complete case scenario (i.e. where patients with a missing outcome are excluded), P₁ and P₂ are the proportion of patients who were excluded in groups 1 and 2 respectively, and Y₁ and Y₂ are the proportion of patients in treatment group 1 and 2 with missing data who are assumed to experience an event (i.e. who experience the primary outcome). For this sensitivity analysis, we will consider all patients who were excluded from the primary analysis due to missing data. We assume that the standard error for Δ is approximately equal to the standard error for Δ_{CC} .

 Y_2 will be varied between 10%, 25%, 50%, 75%, and 90% and for each value of Y_2 , Y_1 will be varied between Y_2 -10%, Y_2 , and Y_2 +10%. For example, for Y_2 =25%, Y_1 will vary between 15%, 25%, and 35%.

For each scenario, a treatment effect and 95% confidence interval will be calculated, which will be compared with results from the main analysis of the primary outcome to see if conclusions are affected by different assumptions regarding the missing data.

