5. ANALYSIS PRINCIPLES

5.1 General principles for analysis

The primary analysis for each outcome will be by intention-to-treat, meaning that all patients on whom an outcome is available will be included in the analysis, and will be analysed according to the treatment group to which they were randomised. More information on which patients are considered to have an available outcome is available in later sections. All tests will be two-sided, and will be considered statistically significant at the 5% level.

For each analysis, the following summaries will be provided:

- The number of patients in each treatment group who are included in the analysis
- The mean (SD) or median (IQR) in each treatment group for continuous outcomes, or the number (%) of patients experiencing an event for binary or time-to-event outcomes (time-to-event outcomes will also present the median time to event in each treatment arm if applicable)
- The treatment effect (difference in means for continuous outcomes, odds ratio for binary outcomes, hazard ratio for time-to-event outcomes, rate ratio for count outcomes) with its 95% confidence interval and a p-value

All analyses will adjust for the minimisation variables (type of underlying malignant disease [mesothelioma, lung cancer, breast cancer, other] and WHO performance status [0-1 or 2-3]).[6-8] Minimisation variables will be included as covariates in the regression model for each outcome.

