5.3 Analysis of primary outcome

The primary outcome (pleurodesis failure at 90 days post randomisation) will be analysed using a logistic regression model. As specified above, the model will adjust for the minimisation variables, and will exclude patients with missing outcome data.

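### The missing-not-at-random formula for the primary outcome omits the observed event rates and adds proportions to an odds-ratio effect, so its results are wrong

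*SAP*

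**What the plan says.** Section 5.7.1 of the SAP defines the treatment effect under a missing-not-at-random scenario as Δ = Δ_CC + Y1P1 − Y2P2. Its terms are:

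- Δ_CC "is the treatment effect under a complete case scenario". No scale is named.
- P1 and P2 "are the proportion of patients who were excluded in groups 1 and 2 respectively".
- Y1 and Y2 "are the proportion of patients in treatment group 1 and 2 with missing data who are assumed to experience an event".

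Y2 "will be varied between 10%, 25%, 50%, 75%, and 90" per cent, with Y1 set 10 points below, equal to, or 10 points above Y2: 15 scenarios. In the worked example with Y2 at 25%, Y1 "will vary between 15%, 25%, and 35" per cent. Y is therefore an absolute event proportion, not a difference from the observed rate.

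The standard error of Δ is taken to equal that of Δ_CC. Each scenario yields an effect and a 95% interval, "which will be compared with results from the main analysis of the primary outcome".

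Section 5.1 fixes the reported effect as "odds ratio for binary outcomes". Section 5.3 states that the primary outcome "will be analysed using a logistic regression model", leaving out patients whose outcome is missing. No risk difference is specified anywhere in the SAP.

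**The concern.** There are two separate faults.

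**Wrong quantity.** The formula adds the assumed events among missing patients but leaves the observed patients at full weight. A basic requirement is that if missing patients fail at exactly the observed rates, the answer equals the complete-case effect. In general the formula does not meet it.

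**Wrong or unstated scale.** A weighted sum of proportions has meaning on a risk difference. The effect this SAP defines for the primary outcome is an odds ratio. Adding a few hundredths to an odds ratio or its logarithm does not represent the assumed events.

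The primary analysis drops patients with missing outcomes, and section 5.7 offers no other check on that choice. A check that gives a shift where there is none, or that barely moves under extreme assumptions, can mislead readers about how robust the trial's main result is.

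**Working it through.** **Inputs.** From SAP section 3: failure 10% (poudrage) and 25% (slurry), 10% loss, 165 patients per arm. Section 5.7.1 gives no numerical result to reproduce. The section 3 total does reproduce: 146 per arm with continuity correction, 292 in all, 292/0.9 = 324.4, so 325. Assumptions of mine: group 1 is poudrage (section 5.7.1 does not say), and the splits of missing data by arm other than 10%/10% are illustrative.

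**Algebra.** With observed rate μ, proportion missing P and event rate Y among the missing, an arm's all-randomised risk is (1−P)μ + PY = μ + P(Y−μ). Hence

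Δ = Δ_CC + P1(Y1−μ1) − P2(Y2−μ2).

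The SAP formula minus this is P1μ1 − P2μ2, whatever Y is. It vanishes only when P1μ1 = P2μ2, for example with equal missingness and equal observed rates.

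**Risk-difference scale (percentage points).**

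| μ1 / μ2 | P1 / P2 | Y1 / Y2 | SAP formula | Correct | Error |
|---|---|---|---|---|---|
| 10 / 25 | 10 / 10 | 25 / 25 | −15 + 2.5 − 2.5 = −15.0 | −15 + 1.5 − 0 = −13.5 | −1.5 |
| 10 / 25 | 10 / 10 | 10 / 25 (as observed) | −15 + 1.0 − 2.5 = −16.5 | −15.0 | −1.5 |
| 10 / 25 | 5 / 15 | 25 / 25 | −15 + 1.25 − 3.75 = −17.5 | −15 + 0.75 − 0 = −14.25 | −3.25 |
| 10 / 25 | 15 / 5 | any | | | 1.5 − 1.25 = +0.25 |
| 25 / 25 | 15 / 5 | 25 / 25 (as observed) | 0 + 3.75 − 1.25 = +2.5 | 0 | +2.5 |

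The second row is not on the plan's grid; it is the logical test. The last row is on the grid.

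**Odds-ratio scale**, μ = 10% / 25%, complete-case OR = (0.10/0.90)/(0.25/0.75) = 0.333, log OR −1.099.

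- P = 10% / 10%, Y1 = 100%, Y2 = 90%. Combined risks are 0.09 + 0.10 = 0.19 and 0.225 + 0.09 = 0.315. Correct OR = (0.19/0.81)/(0.315/0.685) = 0.510. The SAP term is 0.10 − 0.09 = 0.01, giving exp(−1.099 + 0.01) = 0.337 on the log scale, or 0.333 + 0.01 = 0.343 if added to the OR itself.
- P = 15% / 5%, same Y. Combined risks are 0.235 and 0.2825, correct OR 0.780. The SAP term is 0.15 − 0.045 = 0.105, giving 0.370 on the log scale.
- All 15 scenarios at P = 10% / 10%: the correct OR runs from 0.32 to 0.51. The formula runs from 0.330 to 0.337 (log OR) or from 0.323 to 0.343 (OR). The largest log-scale shift, 0.01, is about 3% of the log OR's standard error of 0.33.

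**Effect on the conclusion**, unadjusted, 148.5 observed per arm, using the plan's standard-error assumption.

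- At 10% versus 25%, P = 10% / 10%, Y1 = Y2: SAP −15.0 (−23.5 to −6.5), correct −13.5 (−22.0 to −5.0). Same conclusion.
- At an illustrative 15.5% versus 25%, same P, Y1 = Y2: SAP −9.5 (−18.6 to −0.4), correct −8.55 (−17.6 to +0.5). The conclusion differs.

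**The case against.** The strongest reply concerns size. At the planning rates with 10% missing per arm, all 15 corrected risk differences lie between −14.5 and −12.5 points, and every interval excludes zero. The flip above needs a borderline rate that the SAP does not give. The 10% is a planning allowance, and section 5.6.1 counts the primary outcome as missing only if there is no failure information at all in the 90 days, so real missingness may be lower. The error shrinks in proportion: 0.75 points at 5% missing per arm. It is only 0.25 points at 15%/5%. All of this stands and limits the size.

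Second, section 5.7.1 names no scale, and additive proportions suggest that a risk difference was meant. Then the odds-ratio figures fall away, and they come from the extreme corner of the grid in any case. But sections 5.1 and 5.3 define the effect as an odds ratio and no risk difference is specified, so the gap is real; the first fault remains on either reading.

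Third, the group labels are assumed. Tables 3 and 4 show slurry versus poudrage. Swapping the labels reverses the sign of the risk-difference error but not its size. The extreme-corner OR becomes 2.19 (inverse 0.456) instead of 0.510.

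Fourth, the narrow 10-point gap between Y1 and Y2 is a design choice. With 10% missing in each arm, the corrected formula also moves the risk difference by only ±1 point over that gap. I agree, and do not count the grid as an error.

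**Conclusion.** The concern holds. As written, the formula uses event proportions where it needs missing-minus-observed differences. It is wrong by P1μ1 − P2μ2, which is 1.5 points at the plan's own rates and loss, and 3.25 points if missingness splits 5%/15%. That part rests on algebra and on the SAP's own definition of Y. The scale fault rests on reading Δ_CC as the effect fixed in sections 5.1 and 5.3; on that reading the planned scenarios hardly move the estimate and would reassure falsely.

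The primary estimate, interval and test are unaffected, and the error need not change the conclusion. It must still be corrected, because a prespecified rule gives wrong results in the only sensitivity analysis in section 5.7. The competing-risk analysis of time to failure is a separate secondary outcome and does not replace it.

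**What to change.** Replace the formula in section 5.7.1 with Δ = Δ_CC + (Y1−μ1)P1 − (Y2−μ2)P2, where μ1 and μ2 are the failure proportions among patients with observed outcomes. State that Δ_CC is an adjusted risk difference standardised from the primary logistic model, take μ1 and μ2 on the same basis, and report that complete-case risk difference beside the scenarios so that like is compared with like. State which arm is group 1.

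If the odds ratio is to be kept, form each arm's combined proportion (1−P)μ + PY and recompute the OR from those, or impute events at the assumed rates and refit the logistic model.

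Optionally, vary Y1 and Y2 independently from 0% to 100% and report the point at which the conclusion changes. This would stress the result more, but it is not needed to correct the error.

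The cost is SAP wording and a few lines of code; no new data are needed.

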3. SAMPLE SIZE

Previous literature and our own audit data suggest that patients with a WHO performance status score of 2 or better have approximate pleurodesis failure rates of 10% with a thoracoscopy, and 30% with standard chest tube and talc slurry pleurodesis.[5]

In order to detect a 15% difference in pleurodesis failure at 3 months (10% thoracoscopy and poudrage vs. 25% chest drain and talc slurry) with 90% power, a 5% significance level, and 10% loss to follow-up, we would require 325 patients. This has been rounded up to 330 patients (165 patients in each treatment arm).

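### The missing-data sensitivity grid (SAP 5.7.1) caps the gap between the arms' missing patients at 10 points, so with similar loss it barely moves the result and does not locate a tipping point

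*SAP*

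**What the plan says.** Section 5.7.1 of the SAP sets the only planned sensitivity analysis for missing primary-outcome data. The adjusted effect is the complete-case effect plus Y1·P1 minus Y2·P2. P1 and P2 are the proportions excluded in each group, and Y1 and Y2 are the assumed failure proportions among those excluded. Y2 is "varied between 10%, 25%, 50%, 75%, and 90% and for each value of" Y2 there are three values of Y1: Y2 − 10 points, Y2, and Y2 + 10 points. That gives 5 × 3 = 15 scenarios. The standard error is held at its complete-case value. Each estimate and 95% confidence interval is then "compared with results from the main analysis of the primary outcome to see if conclusions are affected by different assumptions regarding the missing data".

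Section 3 gives the planning assumptions. The failure rates to be told apart are "10% thoracoscopy and poudrage vs. 25% chest drain and talc slurry". For that difference the SAP asks for 325 patients, at 90% power and the 5% level and after allowing for 10% loss, and raises this to 330, or 165 per arm. The 10% loss is not split by arm. Section 5.1 states that "All tests will be two-sided, and will be considered statistically significant at the 5% level", and names the effect measure as "odds ratio for binary outcomes".

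**The concern.** A missing-not-at-random analysis is useful when it varies the quantity that could bias the comparison. Here that is mainly the difference in failure between the missing patients of the two arms. The grid varies the common level of failure widely (10% to 90%) but holds the between-arm difference within 10 points. When the two arms lose similar proportions, the common level drops out and only the narrow difference remains.

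The range is narrower than the SAP's own expectations. Section 3 plans on a 15-point difference and quotes earlier rates of 10% and 30%, a 20-point difference. Neither gap, nor its reverse, can occur among missing patients in any of the 15 scenarios. The trial is open-label and section 1.4 acknowledges the greater potential for bias, so missingness that depends on arm is a natural question to ask. If the conclusion is unchanged in all 15 scenarios, the reader learns only that a gap of up to 10 points does not matter, and not what gap would.

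**Working it through.** **Inputs.** Failure 10% vs 25%, 90% power, 5% level, 10% loss, 165 per arm (section 3); two-sided tests (5.1); formula, grid and fixed standard error (5.7.1). Assumptions not in the SAP: group 1 is poudrage, loss is 10% in each arm unless stated, and the effect is an unadjusted risk difference with a Wald interval.

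**Reproducing the planned size.** The two-proportion formula gives 133 per arm without continuity correction and 146 with it. With correction, 2 × 146 = 292, and 292 / 0.9 = 324.4, rounded up to 325. This matches the SAP.

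**Largest shift, equal loss.** With P1 = P2 = P, the shift is P × (Y1 − Y2). At P = 0.10 it lies between −0.10 × 0.10 and +0.10 × 0.10, that is ±1 point, for every value of Y2.

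**Compared with the precision.** Analysed patients per arm: 165 × 0.9 = 148.5. Standard error at the planned rates: √[(0.10 × 0.90 + 0.25 × 0.75) / 148.5] = 0.0432. So 1 point is 0.01 / 0.0432 = 0.23 standard errors, and the smallest significant difference is 1.96 × 0.0432 = 8.5 points.

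**Share of significant results that lose significance after a 1-point shift towards no effect** (exact binomial enumeration, 148 per arm):

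| True failure, poudrage vs slurry | Share changed |
|---|---|
| 10% vs 25% | 4% |
| 15% vs 25% | 15% |
| 20% vs 25% | 28% |
| 25% vs 25% | 38% |

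A simulation of 20,000 trials at 10% vs 25% also gives 4.0%.

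**Unequal loss.** With 12% loss in poudrage and 8% in slurry, the scenario Y1 = 100%, Y2 = 90% gives 1.00 × 0.12 − 0.90 × 0.08 = +4.8 points; the simulation then has about 30% of significant results changed at 10% vs 25%. With the losses swapped (8% and 12%), the largest shift towards no effect is only 0.4 points (Y1 = 20%, Y2 = 10%: 0.016 − 0.012).

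**Worked case, printed formula.** Suppose 12% vs 24% is observed with 10% loss per arm.
- Standard error: √[(0.12 × 0.88 + 0.24 × 0.76) / 148.5] = 0.0440, so z = −0.12 / 0.0440 = −2.7.
- Worst scenario: −0.12 + 0.01 = −11.0 points. The 95% interval is −0.110 ± 0.086, or −19.6 to −2.4 points, still significant.
- Tipping gap: (0.120 − 1.96 × 0.0440) / 0.10 = 0.34, so missing poudrage patients would have to fail about 34 points more often than missing slurry patients.
- If the complete-case risks are weighted by 1 − P, the starting point is 0.9 × (−0.12) = −0.108 and the gap is (0.108 − 0.0863) / 0.10 = about 22 points.

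Both tipping gaps lie outside the grid, so the planned output would show neither.

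**The case against.** A reader might infer that the grid would pass nearly every significant result as robust. The documents do not support that:

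- Section 5.7.1 states no pass/fail rule. It asks only that the scenarios be compared with the main analysis.
- The 4% figure belongs to the planned effect with equal loss. With smaller true effects, more significant results lie near the boundary and the grid changes 15% or more of them.
- P1 and P2 are defined separately by arm, and nothing in the SAP says loss will be equal. When more poudrage than slurry patients are lost, the wide range of Y2 has a real effect.

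It is also tempting to judge the plan against a full 0–100% grid, which in the simulation overturns 77% of significant results at the planned effect with the printed formula. That is not a fair standard, because much of it comes from implausible corners such as every missing poudrage patient failing and no missing slurry patient failing. For an observed difference of 15 points, the tipping gap is (0.15 − 0.0847) / 0.10 = about 65 points, and leaving such a result standing is reasonable. In the worked case, a 34-point gap against poudrage, when observed poudrage patients fail 12 points less often, is a 46-point reversal and not a small departure. Adding only the reversed 15-point gap would move the estimate 1.5 points instead of 1.0 and raise the share changed from about 4% to about 6%.

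Finally, section 5.6.1 counts the outcome as missing only when there are no failure data in the first 90 days, so actual loss may be below 10%, and an open-label design does not by itself show that gaps above 10 points are likely.

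These points limit the size of the problem. They do not change the fact that the between-arm gap is capped at 10 points and that no tipping point is planned.

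**Conclusion.** The concern stands as a weakness in the design of the sensitivity analysis; it leaves the primary analysis untouched. With similar loss in the two arms, the 15 scenarios amount to a shift of at most 1 point at 10% loss, about 0.2 standard errors. They change the conclusion for about 4% of significant results at the planned effect, about 15% at 15% vs 25%, and about 30% at the planned effect with 12% poudrage and 8% slurry loss. The grid excludes gaps of 15 points in either direction and, when no scenario changes the conclusion, leaves the decisive gap unknown.

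These sizes rest on an unadjusted risk difference. The SAP plans an adjusted logistic model reported as an odds ratio and does not say on which scale the formula is applied. If the same 0.01 were added to a log odds ratio, only about 0.5% of significant results would change at the planned effect. The size also depends on using the formula as printed: weighting the complete-case risks by 1 − P raises the 4% to about 9%.

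**What to change.** In section 5.7.1, vary Y1 and Y2 independently over a wider range (for example 0% to 100% in steps of 10 points), and state that the calculation is on the risk-difference scale. Keep the existing 15 scenarios as a marked subset. Report the tipping point, meaning the smallest Y1 − Y2 at which the 95% confidence interval includes no effect. If loss differs by arm, show it as a boundary across the table, since the common level then matters too. Add a statement on whether that gap is clinically plausible, and say that the table is not a pass/fail test.

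The cost is one paragraph of SAP text and one extra table or heat map, with no new data. The downside is that extreme corners will often overturn the result, so the tipping point needs a plausibility judgement, best made before the results are known.

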5.8 Further studies

In addition to the above, data being collected as part of the TAPPS trial may also be used to undertake further sub-studies, the details of which are beyond the scope of this analysis plan. These may include, but are not limited to:

- A full health economic analysis
- Analysis of genetic markers associated with pleurodesis success or failure

6. DATA SUMMARIES

6.1 CONSORT flow chart

The following information will be provided in the form of a flow chart:

6.2 Summary graphs

The following outcomes will be displayed in the form of Kaplan-Meier survival curves:

- Pleurodesis failure up to 180 days post randomisation (primary outcome)
- All-cause mortality

The following outcomes will be displayed in the form of two adjacent graphs; the first detailing the raw scores for the outcome (beginning with the baseline value) according to each treatment arm, and the second demonstrating the treatment effect. Each graph will indicate 95% confidence intervals (the first graph for the mean outcome at that time point, and the second graph for the treatment effect) and will provide measurements at the 1-month, 3-month and 6-month time points:

- Percentage chest x-ray opacification
- Quality of life measures (EQ-5D and SF-36)
- VAS scores (for breathlessness and thoracic pain)

6.3 Further data summaries

• Incidence of lung entrapment on 18-24 hour CXR

• Incidence of lung entrapment on discharge or drain removal CXR

6.4.2 Table 2 – Results relating to trial interventions and inpatient stay

	Talc slurry (n=)	Talc poudrage (n=)	Number missing (slurry, poudrage)
Duration of procedure			
Grade of operator			
Total fluid drained as			
inpatient			
Complications during			
procedure			
Complications in 2			
hours post talc			
Drain size used (median)			
Thoracic suction used			
Time drain in situ			
Time from randomisation			
to allocated procedure-			
mean (SD)			
Time from allocated			
procedure to discharge-			
mean(SD)			

6.4.3 Table 3 - Results for pleurodesis failure

	Number included in analysis		Summary measure			
Outcome	Slurry (n=)	Poudrage (n=)	Slurry	Poudrage	Treatment effect (Slurry vs. Poudrage) and 95% Cl	P- value
Number experiencing pleurodesis failure at 30 days post randomisation – no. (%)						
Number experiencing pleurodesis failure at 90 days post randomisation – no. (%)						
Number experiencing pleurodesis failure at 180 days post randomisation – no. (%)						
Time to pleurodesis failure from randomisation						

6.4.4 Table 4 – Results for secondary outcomes

	Number included in		Summary measure			
Outcome	Slurry (n=)	Poudrage(n=)	Slurry	Poudrage	Treatment effect (slurry vs. poudrage) and 95% Cl	P- value
All-cause mortality up to 180 days post randomisation						
Hospital inpatient nights up to 90 days						
Thoracic pain – mean (SD)						
7 days						
1 month						
3 months						
6 months						
Breathlessness – mean (SD)						
7 days						
1 month						
3 months						
6 months						
EQ-5D – mean (SD)						

1 month			
3 months			
6 months			
SF-36 – mean (SD)			
1 month			
3 months			
6 months			
Chest x-ray			
opacification – mean			
(SD)			
1 month			
3 months			
6 months			
Adverse events – no.			
(%)			
Serious adverse events			
– no. (%)			

7. **REFERENCES**

- 1. Marel, M., et al., *The incidence of pleural effusion in a well-defined region. Epidemiologic study in central Bohemia.* Chest, 1993. **104**(5): p. 1486-9.
- 2. Heffner, J.E., P.J. Nietert, and C. Barbieri, *Pleural fluid pH as a predictor of survival for patients with malignant pleural effusions.* Chest, 2000. **117**(1): p. 79-86.
- 3. Dresler, C.M., et al., *Phase III intergroup study of talc poudrage vs talc slurry sclerosis for malignant pleural effusion*. Chest, 2005. **127**(3): p. 909-15.
- 4. Rahman, N.M., et al., *Intrapleural use of tissue plasminogen activator and DNase in pleural infection*. N Engl J Med, 2011. **365**(6): p. 518-26.
- 5. Rahman, N.M., et al., *Local anaesthetic thoracoscopy: British Thoracic Society Pleural Disease Guideline 2010.* Thorax, 2010. **65 Suppl 2**: p. ii54-60.
- 6. Davies, H.E., et al., *Effect of an indwelling pleural catheter vs chest tube and talc pleurodesis for relieving dyspnea in patients with malignant pleural effusion: the TIME2 randomized controlled trial.* JAMA, 2012. **307**(22): p. 2383-9.
- 7. Kahan, B.C. and T.P. Morris, *Reporting and analysis of trials using stratified randomisation in leading medical journals: review and reanalysis.* BMJ, 2012. **345**: p. e5840.
- 8. Kahan, B.C. and T.P. Morris, *Assessing potential sources of clustering in individually randomised trials.* BMC Med Res Methodol, 2013. **13**(1): p. 58.
- 9. White, I.R. and S.G. Thompson, *Adjusting for partially missing baseline measurements in randomized trials.* Stat Med, 2005. **24**(7): p. 993-1007.

